### **Relevant Standard Operating Procedures**

Data and documents relevant to the statistician will be kept in a Statistical Master File on the R: drive (secure YTU drive) following the directory structure detailed in the YTU SOP “DS01 Directory structure and version control”. Access to this folder will be restricted to the trial statisticians at York Trials Unit ([name] and [name]) and the YTU data management team. Other relevant YTU SOPs or guidance documents that will be followed in the conduct of this trial include: S01 Statistical Considerations; SG02 Statistical Reporting.

## **6. Analysis**

### **Principles**

All analyses will be conducted on intention to treat basis (ITT), including all randomised participants in the groups to which they were allocated. Any post randomisation exclusions will be referred to the independent statistician on the DMEC for approval. Analyses will be conducted in Stata version 13 or later, using 2-sided significance tests at the 5% significance level. Results will be presented with 95% confidence intervals where appropriate. The statistician conducting the analyses will remain blind to treatment group until the primary analysis is finalised and checked by the second statistician.

Any missing data will be reported for all predictor and outcome variables by trial arm and response rates compared. No imputations will be undertaken, and the impact of missing data will be explored as part of secondary analyses of the primary outcome.

### **Trial Progression**

The flow of participants through the trial will be presented in a CONSORT diagram (see Appendix). Summaries of the numbers of participants invited, assessed for eligibility and randomised will be given, and reasons for exclusion will be listed. Reasons for declining to take part in the study will be listed based on any returned decline forms.

The intervention in the collaborative care arm will be described in terms of the number of participants receiving the treatment, the average number of sessions received, average onset of the intervention since randomisation, duration and how many sessions were conducted face to face or over the phone. Reasons for not receiving any collaborative care will be detailed. The number of

case managers delivering the intervention and the average number of participants per case manager will be given.

Frequencies of dropout (death, dropout from treatment, follow-up or trial) will be presented by trial arm. Reasons for dropout, which are available as free text, will be categorised into common themes and frequencies summarised by trial arm.

## **Baseline Data**

All participant baseline data (demographics from the background information form, outcome data from the baseline questionnaire, PHQ-9 and MINI responses from the diagnostic interview) will be summarised descriptively by trial arm for all randomised participants and all participants included in the primary analysis. No formal statistical comparisons will be undertaken. Continuous measures will be reported as means, standard deviations, minimum, maximum and interquartile ranges; and categorical data will be reported as frequencies and percentages.

## **Analysis Population**

The analysis population will include all patients in their randomised groups with available outcome data (for the primary analysis: PHQ-9 at 4 months or 12 months follow-up) as well as complete baseline covariates specified for the analysis.

Data from withdrawn participants were retained up to the date of withdrawal, unless they specifically requested for their details to be removed. Where withdrawal was only from the intervention, follow-up data were continued to be collected. If participants were lost to follow-up due to death or migration, their data were included in the main analysis up to where they have been lost to follow-up.

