## **Analysis of the Primary Outcome**

### ***Primary Analysis***

Unadjusted descriptives of depression severity (PHQ-9) at all follow-up time points will be presented. A covariance pattern linear mixed effects model will be used to compare collaborative care with usual care on PHQ-9 scores at 4 months. Effects of interest and baseline covariates will be specified as fixed effects, and the correlation of observations within patients over time will be modelled by a covariance structure to describe the random effects. The mixed model will provide increased statistical power by utilising all patients with outcomes for at least one follow-up time point.

The outcome modelled will be PHQ-9 at 4 and 12 months. The model will include as fixed effects: time, treatment group and time-by-treatment interaction, adjusting for PHQ-9 at the diagnostic interview and physical/functional limitations (as measured by the baseline SF-12 physical component score). Different covariance structures for the repeated measurements that are available in the analysis software will be explored, and the most appropriate pattern will be used for the final model based on the model information criteria (AIC). The primary endpoint will be the estimate of the effect of the intervention at 4 months, which will be presented with 95% confidence intervals and associated p-values.

Model assumptions of normality of the standardised residuals and of homogeneity of variance of the standardised residuals against fitted values will be checked. If the model assumptions are in doubt,

the outcome data will be transformed prior to analysis. If the specified mixed model fails to converge with the parameters specified as above, individual regressions at each time point will be undertaken instead.

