### **Secondary Analyses**

1) To explore the potential clustering within collaborative care case managers, descriptive statistics of the PHQ-9 at 4 months will be presented grouped by case manager in the intervention arm. The intra-cluster correlation coefficient (ICC) will be calculated to assess between-case-manager variability. The primary analysis will be repeated adjusting for the clustering by case manager by including case managers as a random effect.

2) Any baseline predictors of PHQ-9 scores at 4 months (age, gender, GAD-7, PHQ-15, mental health medication use and previous history of depression based on M.I.N.I. responses) will initially be identified by individual logistic regressions using  $p < 0.10$ , controlling for PHQ-9 at randomisation. Any remaining predictors from a combined regression will be included as covariates in the primary analysis model.

3) In order to investigate the impact of missing data, any baseline predictors of non-response at 4 months follow-up will be included as covariates in the primary analysis model. Non-response will be defined as the absence of a valid PHQ-9 score, and predictors will be identified initially by individual logistic regressions followed by a combined regression using  $p < 0.10$ .

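### The primary analysis discards patients with an observed PHQ-9 when a baseline covariate is missing, which conflicts with the SAP's own description of the analysed set and gives up precision that is easily kept

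*SAP*

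**What the plan says.** Three parts of section 6 of the SAP describe who is analysed, and they do not agree.

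- Principles calls every analysis intention-to-treat, "including all randomised participants in the groups to which they were allocated". The same section states: "No imputations will be undertaken".
- Analysis Population admits patients with an available outcome (for the primary analysis, PHQ-9 at 4 or 12 months) "as well as complete baseline covariates specified for the analysis".
- Primary Analysis justifies the mixed model by the power gained from "utilising all patients with outcomes for at least one follow-up time point".

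The covariates that must be complete for the primary model are the PHQ-9 from the diagnostic interview and the baseline SF-12 physical component score (PCS). Section 4 gives a pro-rating rule for missing PHQ-9 items and no missing-item rule for the SF-12.

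Under Secondary Analyses, the second analysis adds baseline predictors of outcome chosen by screening. The third, which is the missing-data analysis, provides that "any baseline predictors of non-response at 4 months follow-up will be included as covariates in the primary analysis model". Both fall under the same complete-covariate rule.

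**The concern.** A patient with an observed primary outcome but a missing SF-12 PCS is included according to Principles and Primary Analysis and excluded according to Analysis Population. With imputation ruled out, nothing brings that patient back. An observed outcome is lost because an adjustment variable is absent, although that variable was measured before randomisation and can be filled without reference to arm or outcome.

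The sensitivity analyses do not repair this. Each covariate they add can only keep the analysed set as it is or make it smaller. The analysis meant to examine missing data may therefore use fewer patients than the primary one, and a shift in the estimate could partly reflect different patients rather than the added adjustment.

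At stake are some precision and a clear statement of who is in the primary analysis.

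**Working it through.** **Inputs (SAP, Sample Size).** Effect 0.3 SD, power 80%, two-sided 5%, ICC 0.02, caseload 20, loss to follow-up 26%, final size 658 (329 per arm).

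**Reproducing the plan's figures.**
- Two-sample t-test at 0.3 SD: 175.4, so 176 per arm and 352 in total.
- Design effect: 1 + (20 − 1) × 0.02 = 1.38; 352 × 1.38 = 485.8, so 486.
- 10% loss: 486 / 0.90 = 540.
- 26% loss: 243 / 0.74 = 328.4, so 329 per arm and 658.

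All four totals reproduce. The 26% covers loss to follow-up only; nothing is reserved for missing covariates.

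**Effect of the complete-covariate rule.** Let m be the share of patients with an outcome who lack a required baseline covariate. The SAP gives no value, so every m below is an assumption.

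- Analysed per arm: n = 329 × 0.74 × (1 − m) = 243.46 × (1 − m)
- Power = Φ(0.3 / √(2 × DE / n) − 1.96)

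DE is taken in two ways: held at 1.38, or recomputed for the smaller analysed caseload as 1 + (20(1 − m) − 1) × 0.02.

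| m (assumed) | Analysed, both arms | Power, DE = 1.38 | Power, DE recomputed |
|---|---|---|---|
| 0 | 487 | 80.4% | 80.4% (DE 1.38) |
| 2% | 477 | 79.7% | 79.9% (DE 1.372) |
| 5% | 463 | 78.4% | 79.0% (DE 1.36) |
| 10% | 438 | 76.2% | 77.4% (DE 1.34) |

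The loss is under one point at 2%, about 1 to 2 points at 5% and 3 to 4 at 10%.

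**Can the loss be avoided?** A simulation of covariate-adjusted linear regression (4,000 replicates) used 352 patients, which is 486 / 1.38, and an effect of 0.3 SD. It assumed correlations with the outcome of 0.5 for baseline PHQ-9 and 0.2 for SF-12 PCS, with only the PCS missing, completely at random.

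| PCS missing | Power, complete cases | Power, PCS filled with pooled mean |
|---|---|---|
| 0 | 91.7% | 91.7% |
| 5% | 90.2% | 91.3% |
| 10% | 87.7% | 91.1% |

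Under these assumptions mean-filling recovers nearly all of the loss. Recovery would be less complete if the missing covariate were the more strongly prognostic interview PHQ-9.

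**The case against.** The other side has good arguments, and several stand.

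- **Principle against definition.** Principles can be read as a rule to analyse as allocated, with Analysis Population as the operational definition. The Baseline Data section describes all randomised participants and those in the primary analysis separately, so the restriction is disclosed. Primary Analysis is explaining the gain over regressions at single time points, as Table 2 confirms, and does not discuss covariates. This softens the conflict with the intention-to-treat wording. It does not remove it: the statement about using all patients with a follow-up outcome becomes untrue once one such patient lacks a covariate.
- **Bias.** A reader might infer that the exclusion biases the comparison or breaks the randomisation. The document does not support that. The covariates precede randomisation, so dropping patients on them does not depend on arm.
- **Rate.** A reader might assume many patients are affected. Under Randomisation, the baseline and interview forms were in the database before allocation, and Data Management and Verification describes completeness checks on each form. Neither guarantees a scorable SF-12, but both argue against a high rate. The protocol or the instrument's standard scoring may also cover missing items.
- **Power.** A reader might conclude that the trial becomes underpowered. The formula ignores the planned covariate adjustment, and in the simulation complete-case power stayed above 80%. Better follow-up than assumed would also offset some loss.
- **Comparability.** It would be too strong to call the sensitivity estimates incomparable with the primary one. Covariates enter only if selected, and the subsets may differ little.
- **Remedy.** Filling covariates cannot be claimed to leave every model's estimate unbiased. The argument from randomisation serves the linear models. In the logistic mixed models the odds ratio is non-collapsible, so filling a prognostic covariate alters the conditional quantity estimated. Filled values could also distort the covariate screening.

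**Conclusion.** The concern holds as a matter of precision and internal consistency. The complete-covariate rule and the blanket bar on imputation together discard observed primary outcomes, contrary to the set described under Primary Analysis and to the wording of Principles. This is a stated rule, not a missing detail, and a nearly costless alternative exists.

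The direction of the loss is certain; its size cannot be settled from the SAP. The power figures rest on assumed missing rates and on the plan's unadjusted formula. They do not show that the sample size is wrong, because all its stated totals reproduce, and they do not show bias between arms. Patients with no follow-up PHQ-9 at all are a separate matter.

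**What to change.** 1. Define the primary set as every randomised patient with a valid PHQ-9 at 4 or 12 months, and bring Principles, Analysis Population and Primary Analysis into line with it.
2. In the linear mixed models, fill a missing baseline covariate with its mean pooled over both arms, without using outcomes; a missing indicator is an alternative.
3. Limit the no-imputation rule to outcomes.
4. In the logistic models for depression caseness and medication, the same filling may be used to keep patients, but the SAP should not claim an unchanged or unbiased conditional odds ratio.
5. Run the covariate screening in the second and third secondary analyses on observed values.
6. Report the number of patients analysed beside each primary and sensitivity estimate, so that any change of set is visible.

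The cost is some SAP wording, a little code, and slightly less adjustment for patients whose covariate is filled. No new data are needed. The rule uses only information from before randomisation, so it can be fixed while the statistician is still blind to allocation.

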## **Analysis of the Primary Outcome**

### ***Primary Analysis***

Unadjusted descriptives of depression severity (PHQ-9) at all follow-up time points will be presented. A covariance pattern linear mixed effects model will be used to compare collaborative care with usual care on PHQ-9 scores at 4 months. Effects of interest and baseline covariates will be specified as fixed effects, and the correlation of observations within patients over time will be modelled by a covariance structure to describe the random effects. The mixed model will provide increased statistical power by utilising all patients with outcomes for at least one follow-up time point.

The outcome modelled will be PHQ-9 at 4 and 12 months. The model will include as fixed effects: time, treatment group and time-by-treatment interaction, adjusting for PHQ-9 at the diagnostic interview and physical/functional limitations (as measured by the baseline SF-12 physical component score). Different covariance structures for the repeated measurements that are available in the analysis software will be explored, and the most appropriate pattern will be used for the final model based on the model information criteria (AIC). The primary endpoint will be the estimate of the effect of the intervention at 4 months, which will be presented with 95% confidence intervals and associated p-values.

Model assumptions of normality of the standardised residuals and of homogeneity of variance of the standardised residuals against fitted values will be checked. If the model assumptions are in doubt,

the outcome data will be transformed prior to analysis. If the specified mixed model fails to converge with the parameters specified as above, individual regressions at each time point will be undertaken instead.

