#### Sample Size

To detect a minimum standard effect size of 0.3 with 80% power and a two-sided 5% significance level would require 352 patients (176 in each group). Although this is an individually-randomised trial, there may be potential clustering at the level of each collaborative care case manager and hence the sample size was inflated to account for this. Based upon an ICC = 0.02 and a caseload size of 20, the design effect would be 1.38 ( $1 + (20 - 1) \times 0.02$ ) and 486 patients (243 in each group) would be required.

The original trial sample size allowed for 10% loss to follow-up, resulting in a total of 540 patients (270 in each group). Following the inspection of interim recruitment figures and disproportionate dropout from the collaborative care arm, this assumption was revised (Substantial Amendment 17). Allowing for a loss to follow-up of 26%, the final sample size needed is 658 patients (329 in each group).

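### The primary mixed model lists no covariate-by-time terms, so each baseline covariate has one slope for 4 and 12 months; freeing the slopes removes a possible small bias at almost no cost.

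*SAP*

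**What the plan says.** Under Primary Analysis, the SAP fits a covariance pattern mixed model to PHQ-9 at both follow-ups and takes the treatment effect at 4 months as the primary endpoint. Its fixed effects are given as follows: "The model will include as fixed effects: time, treatment group and time-by-treatment interaction, adjusting for PHQ-9 at the diagnostic interview and physical/functional limitations", the latter measured by the baseline SF-12 physical component score. No covariate-by-time term is listed. The text does not rule such terms out, but its natural reading is one slope per covariate across both visits.

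If the model does not converge, "individual regressions at each time point will be undertaken instead". That would free the slopes, but only in that event. The missing-data check (Secondary Analyses, item 3) adds baseline predictors of non-response to the same model and mentions no interaction with time. The Quality of Life and Psychological Anxiety sections repeat the primary analysis for the SF-12 component scores and the GAD-7.

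The Departures from the Protocol table explains the move from separate regressions to a mixed model by the wish to use all available data. It does not discuss the slopes. On attrition, the Sample Size section says: "Following the inspection of interim recruitment figures and disproportionate dropout from the collaborative care arm, this assumption was revised".

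**The concern.** A baseline score need not predict the outcome equally well at two visits eight months apart. When one slope has to serve both, the fitted value lies between the two true slopes, and the 4-month comparison is adjusted by the wrong amount. This does no systematic harm while the arms are balanced on the covariate among those who respond. It matters once the 4-month responders in the two arms differ in mean baseline severity, because part of that difference then stays in the treatment effect.

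At stake is a small systematic error in the primary estimate, caused by a restriction that the plan neither needs nor defends. Item 3 of the secondary analyses would not reveal it: interview PHQ-9 is already in the model, so finding that it predicts non-response changes nothing.

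**Working it through.** **The plan's own figures.** Per-arm size for 0.3 SD, 80% power, two-sided 5%: 2 × (1.960 + 0.842)² / 0.3² = 174.4. Adding the t-correction 1.96²/4 = 0.96 gives 175.4, so 176 per arm and 352 in total. Then 352 × 1.38 = 485.8, which agrees with "486 patients (243 in each group) would be required". With 26% loss, 243 / 0.74 = 328.4, so 329 per arm and 658. All reproduce. None of them bears on the slopes.

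**Formula.** Let b4 be the true 4-month slope, b the common fitted slope, and D the collaborative care minus usual care difference in mean baseline PHQ-9 among 4-month responders. The raw difference between responders contains b4 × D and the model removes b × D. Hence

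bias ≈ (b4 − b) × D.

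It is zero if b = b4 (equal slopes) or if D = 0.

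**Inputs, all assumed because the SAP gives none.** Baseline SD 4.5 points; residual SD 3.6 at each visit; within-patient correlation 0.5; loss 36% in collaborative care and 16% in usual care at 4 months (26% overall, matching the plan), 40% and 22% at 12 months. Odds of loss rise by the stated odds ratio (OR) per SD of baseline PHQ-9, in collaborative care only unless noted. One covariate; unstructured covariance; maximum likelihood; 1,000,000 patients per row. Negative bias favours collaborative care. Products use unrounded slopes.

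| Slopes 4 / 12 months | Non-response | b | D | (b4 − b) × D | Bias, points (SD) | Bias with time terms, points |
|---|---|---|---|---|---|---|
| 0.4 / 0.4 | OR 2 | 0.401 | −0.995 | +0.001 | +0.005 (+0.001) | +0.005 |
| 0.45 / 0.35 | OR 2 | 0.402 | −1.011 | −0.049 | −0.065 (−0.016) | −0.018 |
| 0.5 / 0.3 | OR 2 | 0.405 | −1.030 | −0.097 | −0.097 (−0.023) | +0.001 |
| 0.3 / 0.5 | OR 2 | 0.395 | −1.007 | +0.095 | +0.093 (+0.024) | −0.001 |
| 0.6 / 0.2 | OR 2 | 0.414 | −1.003 | −0.187 | −0.190 (−0.042) | −0.002 |
| 0.6 / 0.2 | OR 3 | 0.413 | −1.441 | −0.269 | −0.259 (−0.058) | +0.011 |
| 0.5 / 0.3 | OR 2 both arms, equal loss (26%, 30%) | 0.405 | +0.009 | +0.001 | −0.007 (−0.002) | −0.008 |
| 0.5 / 0.3 | OR 2 both arms, unequal loss | 0.407 | −0.536 | −0.050 | −0.057 (−0.013) | −0.006 |
| 0.5 / 0.3 | unrelated to severity | 0.405 | −0.002 | 0.000 | −0.001 (0.000) | −0.001 |

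Simulation error is about 0.333 × √(658 / 1,000,000) = 0.009 points, so the last column is noise around zero. In the 0.45 / 0.35 row, −0.049 is the better figure for the bias (−0.049 / 4.13 = −0.012 SD).

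**At the planned size** (600 trials of 658):

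- Slopes 0.5 / 0.3, OR 2: mean standard error 0.333 points with a common slope and 0.332 with free slopes; 95% interval coverage 94.5% and 95.3%. The bias is 0.097 / 0.333 = 0.29 of a standard error.
- Slopes 0.6 / 0.2, OR 3: coverage 88.8% and 93.7%.

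A separate set of 600 simulated trials per setting, also with 36% against 16% loss, gave biases of 0.011 to 0.047 SD with a common slope where loss depended on severity, and 0.004 SD or less with free slopes.

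**The case against.** The strongest reply is that main-effect adjustment is a complete and legitimate prespecification, that nothing here contradicts itself, and that the bias is small. This largely stands. For moderate slope differences the bias is about 0.02 SD with near-nominal coverage. A visible loss of coverage needs a slope that falls to a third between visits and a threefold rise in the odds of loss per SD in one arm only.

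Several stronger readings are tempting, and the document supports none of them:

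- *Severity-related dropout from collaborative care is enough to bias the estimate.* It is not. The model conditions on interview PHQ-9, and with equal slopes the bias is nil (first row).
- *The plan reports the harmful kind of dropout.* It reports "disproportionate dropout from the collaborative care arm", with no figures by arm and no link to severity. Unequal loss unrelated to severity gives no bias (last row).
- *Baseline severity predicts 4 months better than 12, so the bias favours collaborative care.* The SAP says nothing about either slope or about who leaves. With the slopes reversed, the sign reverses.
- *The fallback contradicts the primary model.* A fallback used only on non-convergence is expected to be a different model.

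The calculations vary PHQ-9 only. Extending them to the SF-12 physical score rests on the same formula, not on a separate simulation.

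What remains is that the restriction is real, no planned analysis lifts it unless the model fails to converge, and it buys no precision.

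**Conclusion.** The point holds as a minor, conditional one. As listed, the fixed effects impose a common slope for each baseline covariate at 4 and 12 months. The 4-month effect is biased only if two things occur together: slopes that differ by visit, and severity-related non-response that leaves the arms with different baseline severity among responders. The second can arise from a stronger relation to severity in one arm, or from the same relation combined with unequal loss.

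Under the assumed inputs the bias is about 0.01 to 0.05 SD in either direction, or 0.01 / 0.3 = 3% to 0.05 / 0.3 = 17% of the planned effect; the most extreme setting tried reached 0.06 SD. The SAP supplies no evidence that either condition holds, so these figures show what could happen and do not estimate the bias in this trial.

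**What to change.** In Primary Analysis, add interview-PHQ-9-by-time and baseline-SF-12-physical-score-by-time to the listed fixed effects. In the Quality of Life and Psychological Anxiety sections, state that the repeated models also include baseline-by-time terms.

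The cost is one phrase in each place and two more parameters in the primary model, with about 658 × 0.74 = 487 patients expected at 4 months. The standard error is practically unchanged and the sample size is unaffected.
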